## **6.5 Interim Analysis**

No interim analysis is planned.

## **6.6 Timing of Final Analyses**

Data analysis will commence after all subjects have completed the study and the study database is cleaned and locked for the data prior to the extended follow-up. Note the PK and ADA data may be locked separately.

## **6.7 Multicenter Study**

This is a multicenter study. Because of small sample sizes for most of the sites, no by site analysis will be performed. All sites will be pooled for data analysis and summary.

## **6.8 Multiple Comparisons/Multiplicity Adjustment**

To control for the family-wise type-I error rate, the following testing procedures will be implemented:

1. Test the high/low dose (Treatment Groups 1 and 2) combined group against placebo (Treatment Group 3) for the primary efficacy endpoint. If  $p \leq 0.05$  then proceed to
2. Test the high/low dose combined group against placebo for the 1st secondary efficacy endpoint. If  $p \leq 0.05$  then proceed to
3. Test the high/low dose combined group against placebo for the 2nd secondary efficacy endpoint. If  $p \leq 0.05$  then proceed to
4. Test the high dose against placebo for the primary efficacy endpoint. If  $p \leq 0.05$  then proceed to

5. Test the low dose against placebo for the primary efficacy endpoint. If  $p \leq 0.05$  then proceed to
6. Repeat above Steps 4-5 for testing the 1st secondary efficacy endpoint, then the 2nd secondary efficacy endpoint.

In the above sequential testing, if any step has  $p > 0.05$  then the tests of this step and of all subsequent steps will be considered not statistically significant.

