### **3.4 Hypotheses**

The hypothesis to be tested in the study is that AK002, in either one or both of the 2 doses, are different from placebo with regard to the primary endpoint of number of eosinophils per HPF in biopsies from the gastric mucosa.

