### 3.5 Determination of Sample Size

Assuming a reduction of 30% in the number of eosinophils per HPF (primary endpoint) from baseline in the AK002-treated group (Treatment Group 1 or 2) versus a 10% reduction per HPF in the placebo group (Treatment Group 3), and assuming a standard deviation of 20%, 20 subjects per group would provide 87% power with a significance level of 0.05.

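### Section 6.8 controls the 5% error rate but gives away low-dose power: both doses could be tested in parallel within an endpoint, provided both must succeed before the next endpoint opens

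*SAP*

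**What the plan says.** Section 6.8 of the SAP is one fixed sequence with every test at 0.05:

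- Steps 1–3: high and low dose combined against placebo, on the primary, then the 1st secondary, then the 2nd secondary endpoint.
- Step 4: "Test the high dose against placebo for the primary efficacy endpoint".
- Step 5, reached only if step 4 succeeds: "Test the low dose against placebo for the primary efficacy endpoint".
- Step 6: the same high-then-low order on the 1st and then the 2nd secondary endpoint.

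If any step has p > 0.05, "then the tests of this step and of all subsequent steps will be considered not statistically significant".

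Two consequences follow. On each endpoint the low dose can be claimed only if the high dose has been. The dose tests on a secondary endpoint open only if both doses were significant on the endpoint before it.

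Section 3.4 states the study hypothesis as "AK002, in either one or both of the 2 doses, are different from placebo". Section 3.5 sizes the trial for one dose group against placebo. Section 3.6 records that the protocol's high-then-low gatekeeping was revised to add the pooled comparison and to cover the secondary endpoints.

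**The concern.** The hypothesis in section 3.4 allows for either dose working alone, but the sequence can never give a confirmatory claim for the low dose alone. With high-dose p = 0.06 and low-dose p = 0.001 on the primary endpoint, the low-dose result would have to be called not significant.

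A restriction of this kind is worth its price when it protects the error rate. Here the pooled test in steps 1–3 already gives that protection within each endpoint. What is at stake is power for the low-dose claim.

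**Working it through.** **Inputs.** Section 3.5: reduction of 30% on AK002 and 10% on placebo, SD 20%, 20 per group, alpha 0.05. Section 3.2.3: 1:1:1 allocation. Not given in the SAP and therefore assumed: two-sided tests (section 3.4 speaks of a difference), no dropout, effects on the secondary endpoints, and correlation between endpoints. The simulations use unadjusted t-tests, not the ANCOVA and logistic models of sections 7.10 and 7.11.

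**1. The SAP's own figure.** Section 3.5 says "20 subjects per group would provide 87% power". The standardised difference is (30 − 10)/20 = 1. The noncentrality is 1/√(1/20 + 1/20) = 3.162 on 38 degrees of freedom, and the two-sided power is 86.9%. The 87% is reproduced.

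**2. Why high-before-low adds no protection within an endpoint.** If both dose nulls are true on an endpoint, all three arms are equal there, so the pooled null is true as well. Hence, where the pooled null is false, at most one dose null is true, and testing it at 0.05 is enough.

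**3. Error rate over all three endpoints.** Take the rule: both doses in parallel within an endpoint; next endpoint only if both have p ≤ 0.05.

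- *Some pooled null is true.* The first such null is tested at 0.05, and every later test needs its rejection. A false claim requires that one 5% error.
- *All pooled nulls are false.* Each endpoint has at most one true dose null. Take the first endpoint that has one. That null is tested at 0.05, and later endpoints open only if it is rejected. Again, one 5% error is needed.

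Family-wise error is therefore at most 5%. Simulation over several patterns of null and real effects, with endpoint correlation 0 and 0.5, gave at most 5.0% within simulation error.

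**4. What happens without the condition between endpoints.**

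- *Each dose runs its own chain.* Let the high dose be null on the primary only and the low dose null on the 1st secondary only, with large effects elsewhere. All pooled gates pass and two true nulls are each tested at 5%: 1 − 0.95² = 9.75%. Simulated: 9.7% (correlation 0) and 9.6% (0.5).
- *Either dose opens the next endpoint.* With one null dose on each of the three endpoints: 1 − 0.95³ = 14.3%. Simulated: 14.3% (correlation 0) and up to 13.5% (0.5).

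**5. Nothing is lost.** The current rule already requires both doses to succeed before the next endpoint opens. Every test reached and passed now is also reached and passed under the rule in item 3, and this held in every simulated trial. High-dose power on the primary endpoint is unchanged.

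**6. Size of the gain.** Probability of a low-dose claim on the primary endpoint, counting the primary pooled gate only (placebo −10%, SD 20, 20 per arm, 200,000 simulated trials per row):

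| High dose | Low dose | Current order | Parallel | Gain (points) |
|---|---|---|---|---|
| −30% | −30% (SAP assumption) | 78.5% | 86.1% | 7.6 |
| −35% | −30% | 85.4% | 86.8% | 1.4 |
| −40% | −30% | 86.7% | 86.8% | 0.1 |
| −30% | −25% | 59.8% | 63.4% | 3.6 |
| −30% | −20% | 32.6% | 33.6% | 1.0 |
| −25% | −30% | 59.7% | 83.0% | 23.3 |
| −20% | −30% | 32.8% | 73.7% | 40.9 |

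Passing steps 2–3 as well lowers both columns. With an effect of 1 SD for both doses on all endpoints, the first row becomes 70.7% against 77.6% at zero correlation, and about 74% against 81% at correlation 0.5.

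**The case against.** **The sequence is complete and valid.** It is prespecified, it controls family-wise error at 5%, and sections 7.10.1 and 7.11.2 defer to it. A sponsor may choose a high-first order. This stands: a reader might infer from the concern that the SAP inflates the type I error, and it does not. It remains a point worth making because the alternative costs nothing and the SAP gives no reason for the order.

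**The stopping sentence protects across endpoints.** This also stands. A reader might infer that the doses can be freed of each other throughout steps 4–6. Item 4 of the working shows that they cannot: only the order within an endpoint is redundant.

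**The large gains need the high dose to work less well than the low dose.** True. Section 3.5 assumes the same effect for either group, and under section 3.2.1 Group 1 receives at least as much drug as Group 2 at every infusion. The last two rows of the table are assumptions without support in the SAP. The striking split is also rare: with equal effects, a high dose above 0.05 together with a low-dose p of 0.001 or less arose in 1.3% of simulated trials.

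**The practical loss is limited.** The pooled claim survives a high-dose miss, and section 7.10.1 still compares the low dose with placebo. Only the confirmatory status of that result is lost, in a Phase 2 trial.

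**Origin of the order.** It is tempting to call it a leftover from the protocol's high-then-low gatekeeping. Section 3.6 records the revision but gives no reason for keeping the order, so the motive is not known.

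**Conclusion.** The point holds as a free gain in efficiency, not as a flaw in error control. On each endpoint the high-before-low order adds nothing to the protection that the pooled gate gives, and it rules out a low-dose-only claim that section 3.4 allows for.

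Under the SAP's equal-effect assumption the cost is about 7 to 8 percentage points of power for the low-dose claim on the primary endpoint, whether or not the secondary pooled gates are counted. It is about 0–4 points in the scenarios where the high dose works better, and more (for example 60% to 83%) only under an assumed weaker high-dose effect.

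The error-rate result rests on the closed-testing argument and does not depend on the simulation inputs. It does depend on requiring both doses to be significant before the next endpoint opens. The power figures rest on the assumptions listed under the inputs.

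**What to change.** Leave steps 1–3 as they are and replace steps 4–6 with wording such as:

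> After step 3, compare high dose with placebo and low dose with placebo on the primary endpoint, each at 0.05 and neither conditional on the other. Only if both have p ≤ 0.05, compare both doses with placebo in the same way on the 1st secondary endpoint. Only if both have p ≤ 0.05 there, do so on the 2nd secondary endpoint.

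Keep the final stopping sentence for steps 1–3 and for moves between endpoints, and state that it does not apply between the two doses within an endpoint. Do not let each dose run its own chain, and do not let one significant dose open the next endpoint.

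The cost is a change of SAP wording, made before unblinding. It needs no further data and no alpha, and every claim available under the current order stays available. If the sponsor prefers to keep high-first, section 6.8 should give the reason and say that a low-dose-only result will not be claimed as confirmatory.

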## 6.9 Examination of Subgroups

Key endpoints may be summarized by subgroup to explore the heterogeneity of the treatment effect across subgroups. Subgroups to be considered are:

- Randomization stratum (baseline highest weekly PRO average score 3–4.9, 5.0–10.0)
- Subjects with EG or EGE alone, EG + EGE, subjects with EoE
- Gender (Male, Female)
- Age (<45, 45 to <65, 65+)
- Baseline peripheral eosinophil counts (<median vs  $\geq$ median)

## 7. Statistical Analysis

### 7.1 Analysis Populations

The population of “all enrolled subjects” comprises all those who signed informed consent, met all eligibility criteria at Screening, and are randomized to one of the treatment groups.

#### 7.1.1 Safety Population

The safety population comprises all subjects who have signed informed consent and received at least one dose of study drug. All safety endpoints will be analyzed using this population.

#### 7.1.2 Per Protocol Analysis (PP) population

The per protocol population will include all randomized subjects who do not have major protocol deviations adversely affecting the data interpretation. Some examples of PP exclusion criteria are

- Did not receive at least 2 doses of study medication
- Changed dose of systemic steroids and/or started systemic steroid treatment during the study or injections of steroids in the stomach and/or duodenum (this does not include steroids used as premedication the day before and/or the day of study drug infusions).
- Received other prohibited medications (eg, IL-5 inhibitors, dupilumab) potentially impacting efficacy during study treatment

- Did not have at least 6 PROs over 14 day period at any timepoint after administration of second dose.

The study statistician along with the study team will review protocol deviations to identify subjects to be excluded from the per protocol analysis population. The PP exclusion criteria will be updated prior to the database lock and unblinding. The PP population will be specified prior to unblinding using said exclusion criteria.

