#### **3.2.2 Duration of Study**

Total subject duration on study is approximately 23–25 weeks.

- Screening phase: 21–35 days
- Treatment phase: 85 days ( $\pm 3$  days)
- Follow-up after last dose: 56 for subjects who do not enroll in the AK002-003X extension study or 28 days ( $\pm 3$  days) for subjects who enroll in the AK002-003X extension study. If the absolute lymphocyte or eosinophil counts have not recovered by Day 141, the follow-up period will be extended, and subjects will be followed until the counts have recovered.

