### 5.2 Secondary Efficacy Endpoint

#### 1st Secondary Endpoint

Proportion of Treatment Responders, defined as patients with >30% reduction in TSS score combined with a >75% reduction in eosinophils in the gastric and/or duodenal mucosa. The eosinophil count is obtained on Day 99 (Week 14) biopsy and the TSS score for the analysis will be the average of the 14 daily scores starting with the day of the last dose to the day before the end of study biopsy. If a minimum of 7 daily scores are not recorded in this nominal 14-day window, the window will be rolled back until a

minimum of 7 scores are present. For patients whose biopsy is collected prior to Day 99 due to early discontinuation, the average of the last 14 days of TSS scores recorded for that patient will be used for the analysis.

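### The Per Protocol steroid exclusion has no end date at the Day 99 biopsy, so applied literally it can remove a subject whose primary and secondary endpoints are already complete

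*SAP*

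**What the plan says.** SAP 7.1.2 defines the PP population as randomized subjects who "do not have major protocol deviations adversely affecting the data interpretation". It then introduces a list with "Some examples of PP exclusion criteria are". Two bullets concern medication:

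- Steroids: "Changed dose of systemic steroids and/or started systemic steroid treatment during the study". The same bullet adds steroid injections into the stomach or duodenum. The only exception is premedication on the day before or the day of an infusion.
- Other prohibited medications: excluded when "potentially impacting efficacy during study treatment".

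On how the list will be used, the section says "The PP exclusion criteria will be updated prior to the database lock and unblinding" and then "The PP population will be specified prior to unblinding using said exclusion criteria".

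The timing comes from other sections:

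- **Primary endpoint (5.1, 7.10.1):** the eosinophil count at the Day 99 biopsy.
- **Secondary endpoints (5.2):** these use that biopsy and/or the TSS averaged over the days "starting with the day of the last dose to the day before the end of study biopsy". If too few scores are present, the window is rolled back, never forward.
- **Study length (3.2.2):** "Follow-up after last dose: 56 for subjects who do not enroll in the AK002-003X extension study or 28 days" for those who do. With the last dose on Day 85, that means Day 141 or Day 113.
- **Efficacy population (3.6, Revision History):** PP replaces MITT, and the ITT population was removed.

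**The concern.** An exclusion for confounding medication should cover the time in which that medication could alter the endpoint. The steroid bullet runs past that time. The bullet on other medications, read with the 85-day treatment phase in 3.2.2, stops short of it.

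The steroid bullet matters more, because it lets an event after the outcome decide who is analysed. A subject with all four doses, a full diary and a valid Day 99 biopsy who starts a systemic steroid on Day 110 meets the bullet as worded. That steroid cannot change any value tested in the hierarchy of 6.8.

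A late start may reflect continuing disease. If so, removal depends on response, and through response on treatment arm. Fixing the list before unblinding does not prevent this. The time at risk also depends on the subject's choice to enter the extension, which is made after randomization. Removing poor responders from placebo would shrink the treatment difference; removing them from an active arm would inflate it. No other efficacy set is planned in which the effect would show.

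**Working it through.** **1. The windows side by side** (nominal days)

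| Item | Ends | Relative to the biopsy |
|---|---|---|
| Primary endpoint (5.1) | Day 99 | at the biopsy |
| TSS part of the secondary endpoints (5.2) | Day 98 | day before |
| Steroid bullet, extension subjects | Day 113 | 113 − 99 = 14 days after |
| Steroid bullet, other subjects | Day 141 | 141 − 99 = 42 days after |
| Other-medication bullet, with the 85-day treatment phase of 3.2.2 | Day 85 | 99 − 85 = 14 days before |

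The excess is 14/113 = 12% of on-study days for extension subjects and 42/141 = 30% for the others. These are shares of calendar time, not risks of exclusion.

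**2. The plan's own figure** (3.5). Inputs: 30% versus 10% reduction, so a difference of 20 points; SD 20; 20 per group; alpha 0.05, taken as two-sided. The noncentrality is 20 / (20 × √(1/20 + 1/20)) = 3.16 on 38 degrees of freedom. The two-sample t-test then has power 86.9%, which reproduces the stated 87%. For the pooled comparison that opens the hierarchy (40 versus 20), the same formula gives 94.8%.

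**3. Loss of numbers only** (assumed counts, exclusions unrelated to outcome)

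| Removed per arm | One dose vs placebo | Pooled vs placebo |
|---|---|---|
| 0 | 86.9% | 94.8% |
| 1 | 85.1% | 93.8% |
| 2 | 83.0% | 92.5% |
| 3 | 80.7% | 91.0% |

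**4. Worst-case selection.** Suppose the k subjects removed are exactly the k worst of n in one group, with normally distributed outcomes. The group mean then moves by SD × (sum of the k largest expected order statistics of n standard normals) / (n − k).

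| Group | k | Sum | Shift in SD | Shift at SD 20 | Share of 20 points |
|---|---|---|---|---|---|
| n = 20 | 1 | 1.868 | 1.868/19 = 0.098 | 2.0 | 10% |
| n = 20 | 2 | 3.275 | 3.275/18 = 0.182 | 3.6 | 18% |
| n = 20 | 3 | 4.406 | 4.406/17 = 0.259 | 5.2 | 26% |
| n = 40 | 1 | 2.161 | 2.161/39 = 0.055 | 1.1 | 6% |
| n = 40 | 2 | 3.914 | 3.914/38 = 0.103 | 2.1 | 10% |
| n = 40 | 3 | 5.431 | 5.431/37 = 0.147 | 2.9 | 15% |

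The n = 20 rows apply to a single dose arm or to placebo. The n = 40 rows apply to the pooled active group in step 1 of 6.8. In that first test an inflating shift can therefore reach only the n = 40 values. The n = 20 values apply there to placebo alone, where they shrink the difference.

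**The case against.** The best defence is the text around the bullet. The list gives examples of major deviations that harm interpretation of the data, and a steroid started after the biopsy does no such harm to the primary or secondary endpoints. The statistician and study team review deviations, the criteria are to be updated before lock, and 7.3 requires each exclusion to be listed with its reason. The team could therefore keep such a subject, and any removal would be visible.

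This stands in part. A reader might infer that the SAP definitely deletes these subjects; it does not. But the population is to be formed from the stated criteria, and the bullet names this very event as an example. Lead-in and bullet point in opposite directions for the same subject, which leaves the outcome to case-by-case judgement.

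Three other stronger readings also fail:

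- **The window extends into extended follow-up.** The database is locked on data before that period (6.6), and Table 1 schedules no concomitant-medication collection in it. The excess is at most 14 or 42 days.
- **A late steroid start shows treatment failure.** The SAP does not say so. It allows for subjects with asthma, atopic dermatitis or eosinophilic esophagitis (Table 1 notes), so other reasons are possible.
- **No efficacy data after the biopsy could be affected.** Table 1 schedules daily ePRO to Day 141 and a subject-completed clinic assessment on Days 113 and 141. Sections 5.3 and 7.12 include exploratory by-visit analyses. A late steroid could affect those.

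**Conclusion.** The point holds as a mismatch of windows within 7.1.2. The steroid exclusion runs past the biopsy, the neighbouring exclusion stops before it, and neither is tied to the time at which the primary and secondary endpoints are complete. Because PP is the only efficacy population, the literal reading can discard valid data on an event after the outcome.

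The size cannot be determined, because the SAP gives no rate of late steroid starts. If such starts are unrelated to response, the cost is a modest loss of power, roughly 2 points per subject lost from each arm for one dose against placebo. The shifts of 2.0 to 5.2 points (20 subjects) and 1.1 to 2.9 points (40 subjects) are upper bounds: they assume normal outcomes, the planning SD, and removal of exactly the worst subjects in one group only. They should not be read as expected bias. The stated 87% power is not in dispute.

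**What to change.** Make the change in the update of the PP criteria that the SAP already plans before lock and unblinding:

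1. For the primary and secondary analyses, end both medication-based exclusion windows at the Day 99 (or early) biopsy.
2. State that medication events after that biopsy do not exclude a subject from PP for those analyses.
3. For exploratory endpoints that use data after the biopsy, add a separate rule for late steroid use, for example leaving out only the data collected after the steroid start.

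No new data are needed. The cost is a short text change and one extra data-handling rule for the exploratory by-visit analyses. The change concerns the analysis set only and takes no position on whether steroids may be given.

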### 3.6 Changes to Analyses Planned in the Protocol

The protocol-defined gatekeeping procedure of high dose then low dose comparison to placebo for the primary endpoint is revised to include high/low pooled, high, and low dose comparisons to placebo for the primary and secondary endpoints.

The protocol-defined treatment responder is now classified as the 1st secondary endpoint and percent change from baseline to end of treatment in TSS is now the second (2nd) secondary endpoint. Other protocol-defined secondary endpoints are now moved to the exploratory endpoints.

The protocol-defined MITT population is now replaced with Per Protocol population for efficacy analysis.

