## 7.10 Analysis of Primary Efficacy Endpoint

### 7.10.1 Primary Analysis of Primary Efficacy Endpoint

The primary efficacy endpoint is the percent change from baseline to Day 99 in the number of eosinophils per HPF in gastric or duodenal mucosa with biopsy. For subjects who provide gastric or duodenal only biopsy, the calculation will be based on the average count of the highest readings from the respective mucosa at baseline and Day 99. For subjects who provide both gastric and duodenal biopsies, the calculation will be based on the average count of the highest readings from the Day 99 biopsy that correspond in location (gastric or duodenal) to the location with the highest average count at baseline. This endpoint will be summarized by treatment group.

The pooled high/low dose group and each active dose group will be compared to the placebo group in pairwise comparison using analysis of covariance (ANCOVA) model with percent change from baseline as outcome, treatment as factor, and baseline value and randomization stratum as covariates. To control for the type-I error, the Gatekeeping procedure defined in Section 6.8 will be followed.

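### A diary shortfall can remove a subject with valid biopsies from the primary histology test, because one Per Protocol population serves every efficacy endpoint

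*SAP*

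**What the plan says.** Section 3.6 of the SAP sets the efficacy population: "The protocol-defined MITT population is now replaced with Per Protocol population for efficacy analysis". The Revision History records that the ITT population was also removed, so Section 7.1 defines only a Safety and a PP population, besides the set of all enrolled subjects.

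Section 7.1.2 excludes subjects whose major deviations adversely affect interpretation of the data. It introduces its list with "Some examples of PP exclusion criteria are", and one item is "Did not have at least 6 PROs over 14 day period at any timepoint after administration of second dose". It adds that "The PP exclusion criteria will be updated prior to the database lock and unblinding".

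The primary endpoint has no diary component. Section 7.10.1 states: "The primary efficacy endpoint is the percent change from baseline to Day 99 in the number of eosinophils per HPF", taken from gastric or duodenal biopsies.

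The diary enters through the TSS, which is used in both secondary endpoints. Section 5.2 takes "the average of the 14 daily scores starting with the day of the last dose to the day before the end of study biopsy". Its provision for sparse diaries begins "If a minimum of 7 daily scores are not recorded in this nominal 14-day window" and goes on to move the window back until seven scores are found. For subjects whose biopsy is taken early because they discontinued, "the average of the last 14 days of TSS scores recorded for that patient will be used for the analysis".

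**The concern.** A diary criterion makes sense for an endpoint built from the diary. Here it sits in the general definition of the only population named for efficacy, so it also decides who enters the histology comparison. A subject who received all four doses and has both biopsies can be left out of the primary test for a reason unrelated to whether the eosinophil count is valid.

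Two things are at stake. Usable randomized data are lost from a trial of about 20 subjects per arm. In addition, diary completion happens after randomization and may follow symptoms or tolerability, so the exclusion could be related to treatment. The SAP specifies no primary analysis in a broader population that would show whether the exclusions mattered.

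The criterion's wording adds uncertainty about how many subjects are affected. Its closing phrase can mean that a subject is excluded only if no 14-day span after the second dose was adequate, or that any single inadequate span excludes. It gives no end day.

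**Working it through.** **Which rule reaches which endpoint**

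| Item | SAP section | Uses diary data? | Population |
|---|---|---|---|
| Primary: percent change in eosinophils per HPF | 5.1, 7.10.1 | No | PP, through 3.6 (7.10.1 names none) |
| 1st secondary: treatment responder | 5.2, 7.11.1 | Yes (TSS), plus biopsy | PP, through 3.6 |
| 2nd secondary: percent change in TSS | 5.2, 7.11.2 | Yes | PP, through 3.6 |

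The diary criterion therefore applies to all three rows, although only the last two use the diary.

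**Who is excluded under each reading.** Inputs: second dose on Day 29 and last dose on Day 85 (Section 3.1); biopsy on Day 99 (Table 1); daily diary scheduled through Day 141, or to 28 days after the last dose after early termination (Table 1).

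- *One adequate span is enough.* Exclusion requires at most 5 entries in every 14-day span. Days 29 to 98 are 98 − 29 + 1 = 70 days, or five consecutive 14-day spans. An excluded subject thus has at most 5 × 5 = 25 entries in 70 days (36%). With a daily diary this should be uncommon.
- *Any poor span excludes.* Take a complete diary whose last entry is on Day 99. The 14 days ending on Day d run from d − 13 to d and hold 99 − (d − 13) + 1 = 113 − d entries. At d = 107 this is 6; at d = 108 it is 5. The subject fails on Day 108, although the biopsy and the TSS window were complete by Day 99.

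**What a lost subject costs.** Inputs from Section 3.5: reductions of 30% and 10% (difference 20 points), SD 20, 20 per group, significance level 0.05. Sidedness is not stated.

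1. The SAP's figure first. Standard error = 20 × √(1/20 + 1/20) = 6.32; noncentrality = 20/6.32 = 3.16; 38 degrees of freedom. A two-sided t test gives 86.9%, which matches the stated 87%. A one-sided test gives 92.8%, so two-sided is used below.
2. Pooled doses against placebo, the first test in Section 6.8. Standard error = 20 × √(1/40 + 1/20) = 5.48; noncentrality = 20/5.48 = 3.65; 58 degrees of freedom. Power is 94.8%.
3. Now remove k subjects from every arm. The values of k are assumptions, because the SAP gives no rate of diary failure.

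| k lost per arm | One dose vs placebo | Pooled doses vs placebo |
|---|---|---|
| 0 | 86.9% | 94.8% |
| 1 | 85.1% | 93.8% |
| 2 | 83.0% | 92.5% |
| 3 | 80.7% | 91.0% |
| 4 | 78.1% | 89.2% |

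One subject is 1/20 = 5% of an arm, or 1/40 = 2.5% of the pooled active group. The table covers lost numbers only. Any bias from selective exclusion cannot be sized from the SAP.

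**The case against.** The best defence is that the list is illustrative and open. Deviations are reviewed and the population is fixed before unblinding, and excluded subjects are listed with reasons (Section 7.3). The opening sentence of Section 7.1.2 also limits exclusion to deviations that harm interpretation, and a diary that lapses after Day 99 would not obviously qualify. The negative wording most naturally means that the subject never had an adequate span, which makes exclusions rare. All of this stands and limits the size of the problem. It does not change what the present text permits: review before unblinding prevents exclusions chosen with knowledge of treatment, but it does not restore a valid biopsy to the primary test.

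Two stronger readings are tempting, and the SAP does not support them.

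- A reader might infer that six entries in Section 7.1.2 contradict seven in Section 5.2. They do different jobs. Six is a population criterion, while seven triggers a roll-back and excludes nobody.
- A reader might infer that the criterion both admits subjects without end-of-treatment diary data and drops subjects with complete data. Those harms belong to opposite readings of the same phrase. Under the lenient reading, old scores can enter the TSS because the roll-back in Section 5.2 has no stated limit, not because of the PP criterion. Under the strict reading, the window before the biopsy must itself hold at least six entries. A check not tied to the final two weeks also suits early discontinuers, whom PP can retain after two doses.

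**Conclusion.** The point holds in limited form. As written, a diary shortfall can remove a subject with valid baseline and Day 99 biopsies from a primary test that uses no diary data. This rests on reading Section 3.6 as covering the primary endpoint, since Section 7.10.1 names no population; nothing in the SAP points to a different one.

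The number affected is unknown. It is probably small on the lenient reading and could be larger on the strict one. The power loss is modest: under the Section 3.5 assumptions, one subject lost from every arm costs about 1.8 points for a single dose against placebo and 1.0 point for the pooled test. Bias is possible, but its direction and size cannot be judged from the document. The correction is worth making before database lock because it is cheap and keeps usable randomized data.

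**What to change.** 1. In Section 7.1.2, state that the diary criterion does not apply to the primary histology endpoint, so that every otherwise eligible subject with valid biopsies is kept there. Apply it only to the two TSS-based endpoints.
2. For those endpoints, state that one adequate 14-day span after the second dose is enough and that entries after the end-of-treatment biopsy are not counted.
3. Make the criterion consistent with the roll-back and early-discontinuation rules in Section 5.2. Do not replace them with an exclusion for fewer than seven scores in the pre-biopsy window: that would cancel the roll-back, which retains exactly those subjects, and would disregard the separate window for early discontinuers.
4. Name the analysis population in Sections 7.10.1, 7.11.1 and 7.11.2.

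The cost is a change of SAP wording before unblinding. The numbers analysed may differ between the primary and TSS-based endpoints, and the tables must show both.
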